- Chest, abdomen and pelvic CT scans will be performed at the treating physicians' discretion. The respective institution's imaging protocols will be followed. Contrast exams will be preferred if there is no contraindication to contrast.
- Baseline CT Scans will be performed and then again every 8 weeks thereafter until disease progression or 2 years – whichever comes first.
- If CT Scans are performed within four (4) weeks after discontinuing pioglitazone, then they do not have to be repeated if the investigator's deems it unnecessary.
- (UT Southwestern and PHS patients ONLY) MRI Abdomen non-contrast will be performed at the Roger's MRI (Department of Radiology) at baseline (7 days before starting therapy with pioglitazone or within 7 days of starting pioglitazone) and a second scan after the end of treatment at week 8 (to be done within 2 weeks of ending pioglitazone). If a patient is unable to complete 8 weeks of pioglitazone but has completed 6-8 weeks of therapy, a follow up MRI will be ordered (also to be done within 2 weeks of ending pioglitazone)

H. Routine and Exploratory Lab Assessments

- Blood for routine CBC, chemistry will be drawn per the laboratory protocol and performed in the clinical laboratory of the respective institutions. Results will be recorded as reported in the electronic medical record.
- A Standard 75 gram oral glucose tolerance test will be performed and blood collection for glucose levels will be obtained prior to the ingestion of the solution (pre-dose (0 hr) and at 2 hours following ingestion). Insulin levels at 0 hr (fasting at least 8 hours) and 2 hours post ingestion will be used to calculate insulin resistance . Record the date of collection, time of collection, and subject ID, on the blood collection source document for exploratory labs. All samples should be labeled for each time point for each patient per study visit. Specimen labels will be provided to each site for each patient.
- The following exploratory labs will be collected in a serum separator tube and sent to [name] laboratory for evaluation:
 - **Adiponectin Levels** : performed at the UT Southwestern Metabolic core as described previously [1]
 - **Insulin level** at 0 and 2 hours: Analysis will be performed at the UT Southwestern Metabolic Phenotypic core as described previously [1]
 - **Monocyte Chemoattractant Protein-1 (MCP-1)** performed at the MagPix multiplexing matching housed at the UT Southwestern Metabolic Core [2]
 - **PAI-1** performed at the MagPix multiplexing matching housed at the UT Southwestern Metabolic Core [2]
- Prior to shipment, complete the sample inventory logs for each patient so that specimen chain of custody can be established. Include in each batch shipment copies of; 1) the blood collection source documents for each patient; and 2) copies of each subjects specimen inventory form. Keep originals of these documents in the patient chart. Please see appendix XX, Specimen Processing and Shipment Instructions for further details.

Patients accrued at VA North Texas will have sample collected at the respective sites, frozen at -20 to -80 C and shipped on dry ice in batches to the UTSW Metabolic Core via overnight courier FedEx (FedEx number:370843180) to the following address

[name] Laboratory
 Touchstone Diabetes Center
 Department of Internal Medicine
 The University of Texas Southwestern Medical Center
 [name]
 [name]
 [name]
 [contact]
 [contact]

H. Schedule of Events

Procedures	Screening ¹	Baseline	2-Weeks	4-weeks	6-Weeks	8-Weeks	End of Treatment or Early-Term (EOT/ET)	14 –Day Follow-up ³
Informed Consent	X							
I/E & Medical History	X							
Concomitant Medications Review / AE Assessment	X	X	X	X	X	X		
Physical Exam	X		X	X	X	X	X	X
Height (cm) ² and Weight Measurement (Kg)	X		X	X	X	X	X	X
Performance status (ECOG)	X	X	X	X	X	X	X	X
Hematology ⁴		X	X	X	X	X	X	X
Serum Chemistry ⁵		X	X	X	X	X	X	X
Serum pregnancy test	X	X						
CA 19-9		X		X		X	X	X
C-reactive protein		X	X	X	X	X	X	X
Serum fasting glucose		X		X		X	X	X
Glucose tolerance		X		X		X	X	X
Adiponectin		X	X	X	X	X	X	X
Insulin level		X ⁶	X	X ⁶	X	X ⁶	X	X
2 hour insulin level		X		X		X	X	X
MCP-1		X	X	X	X	X	X	X
Chest x-ray or Chest CT scan	X					X	X ⁷	X
CT scan of abdomen and pelvis	X					X	X ⁷	X
Toxicity Assessment		X	X	X	X	X	X	
FACT-Hep Questionnaire		X		X		X	X	X
MRI abdomen noncontrast		X ⁸					X ¹⁰	

1. Within 28 days before starting pioglitazone/Day 1 for control arm
2. Height performed at screening only
3. Within 14 days after discontinuing pioglitazone/week 8 for control arm

4. Hematology: CBC with differential and platelet count
5. Serum chemistry: Na, K, Cl, Ca, bicarbonate, BUN, creatinine, AST, ALT, alkaline phosphatase, total bilirubin, total protein, albumin
6. To be performed in conjunction with glucose tolerance test at 0 hr baseline and 2 hr post ingestion.
7. Chest x-ray must be posterior to anterior (PA) and lateral (LAT) plain chest x-ray.
9. 8. If performed within four (4) weeks of discontinuing pioglitazone, then not required to be completed (at the discretion of the investigator).. MRI will be done at Roger's MRI. Baseline MRI to be done before start of pioglitazone or within the first 7 days of starting pioglitazone (UT Southwestern and PHHS patients ONLY)
10. Follow up MRI can be done within 14 days of end of treatment. If patient does not complete 8 weeks but has completed 6-8 weeks of therapy, a follow up MRI should be done as if completed 8 weeks. MRI will be done on 8-10 patients chosen at PI/investigator discretion. (UT Southwestern and PHHS patients ONLY).

XIV. **Treatment Duration (N/A for control arm)**

Treatment will be continued for no more than **8 weeks** of therapy or unless the following events take place:

1. Patient withdraws consent.
2. Intercurrent illness that prevents further administration of pioglitazone
3. Unmanageable adverse events related to pioglitazone
4. General or specific changes in the patient's condition that in the judgment of the physician renders the patient unacceptable for further treatment with pioglitazone
5. Patient is lost to follow-up. Patient refuses to complete study procedures and scheduled appointments.
6. Patient requires more than two dose reductions
7. Interruption in study drug administration for greater than 14 days
8. Closure of the trial as deemed necessary by the principal investigator (PI), the UT Southwestern Institutional Review Board (IRB), the Simmons Comprehensive Cancer Center Data and Safety Monitoring Committee (DSMC) or the U. S. Food and Drug Administration (FDA).

XV. **Withdrawal of Subjects**

Patients can withdraw voluntarily if they are unable to continue with the treatment or for any other reasons. Patients will be encouraged to discuss withdrawal with their physician and the study team.

Patient who withdraw voluntarily will not be followed.

XVI. **Efficacy Assessments**

The following outcome measures are required to evaluate the safety and efficacy of pioglitazone:

1. Measurement of insulin resistance biomarkers: serum adiponectin level, oral glucose tolerance test, and fasting serum levels of glucose and insulin every four weeks.
2. The oral glucose tolerance test will be performed on the initial visit and every four weeks, in fasting state (at least 8 hrs). Patients will be asked to drink a standard glucose solution containing 75 g of carbohydrate. Blood glucose will be obtained prior to the ingestion (0 hr baseline) of the solution, and at 120 min (2 hr) following the ingestion. Blood samples are collected for glucose levels.
3. Documentation of weight. We will measure weight every week in all patients receiving pioglitazone. (See Appendix 2)

4. Documentation Eastern Oncology Cooperative Group (ECOG) performance status. We will determine the ECOG performance status every week in all patients receiving pioglitazone. (See Appendix 1)
5. Measurement of changes in symptoms and quality of life using the FACT-Hep Scale, version 4. (See Appendix 4).
6. RECIST Criteria will be used to determine response. At the time of every tumor assessment and at the time of study discontinuation, assignment of response to one of three categories will be made; complete response (CR), partial response (PR) or progressive disease (PD). Evaluation of measurable and non-measurable lesions in relationship to the baseline tumor assessment will be used to determine response as follows.
7. *MRI will quantitate changes in a) intratumoral fat deposition in pancreatic cancer and b) visceral/subcutaneous fat distribution in pancreatic cancer patients treated with pioglitazone in this phase II study. To determine intratumoral fat content, we will use a previously described advanced chemical shift-based gradient-echo MRI technique that measures the proton density fat fraction (PDFF) [21]. In addition, MRI will allow quantitative determination of body fat volume in the abdomen e.g. subcutaneous/visceral adipose tissue (SAT/VAT) depots, which have been shown to have an important role in insulin resistance [22, 23].*

XVII. Response Criteria

Evaluation of Target Measurable Lesions

Complete Response (CR): Disappearance of all target lesions.

Partial Response (PR): At least a 30% decrease in the sum of the longest diameter (LD) of target lesions, taking as reference the baseline sum LD.

Progressive Disease (PD): At least a 20% increase in the sum of the LD of target lesions, taking as reference the smallest sum LD recorded since the treatment started, or the appearance of one or more new lesions.

Stable Disease (SD): Neither sufficient shrinkage to qualify for PR nor sufficient increase to qualify for PD, taking as reference the smallest sum LD since the treatment started.

Evaluation of Non-Measurable Lesions

Complete Response (CR): Disappearance of all non-target lesions and

normalization of tumor marker level

Incomplete Response/Stable Disease (SD): Persistence of one or more non-target lesion(s) or/and maintenance of tumor marker level above the normal limits

Progressive Disease (PD): Appearance of one or more new lesions and/or unequivocal progression of existing non-target lesions.

All CR or PR cases must be confirmed with follow-up tumor assessments done more than 4 weeks from the assessments that formed the basis for a response. The follow-up assessment must also meet the criteria for CR or PR in relation to baseline assessments.

Time to disease progression (TDP) is a secondary endpoint of this study. All patients should be followed for disease progression every month for the first six (6) months, then every three (3) months thereafter, following discontinuation of study treatment until at least two (2) years after discontinuation of pioglitazone.

XVIII. Data handling and record keeping

The principal investigator will maintain adequate records so that the conduct of the study can be fully documented and monitored. Copies of protocols, case report forms (CRFs), test result originals, all product accountability records, correspondence, subject informed consent, and any other documents relevant to the conduct of the study will be kept on file in the Simmons Clinical Research Office for at least two (2) years after all investigational use of product is discontinued. Study documents must not be destroyed. A record will be kept of all subjects considered and screened for the study and subsequently deemed ineligible. The reason for ineligibility must be recorded.

Case Report Forms (CRFs) will be utilized for each subject entered into the study. Study participants will not be identified by name on any study documents. Subjects will be identified by a subject identification number (see Section XI). The clinical research coordinator will keep the subject code list in a secured locked file cabinet in the Simmons Clinical Research Office. Additionally, all paper documents will be stored in a locked filing cabinet in the Clinical Research Office and all electronic records must be stored on a HIPAA Security Rule-compliant institutional server.

XIX. Safety Monitoring

A. Adverse Event Definition

Adverse Events: Definitions and Reporting

Adverse Events will be reported as indicated by the appropriate following table (see below).

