(MRI will be performed on UT Southwestern and PHS patients ONLY) We propose to evaluate the use of MRI to quantitate changes in a) intratumoral fat deposition in pancreatic cancer and b) visceral/subcutaneous fat distribution in pancreatic cancer patients treated with pioglitazone in this phase II study. To determine intratumoral fat content, we will use a previously described advanced chemical shift-based gradient-echo MRI technique that measures the proton density fat fraction (PDFF) [21]. In addition, MRI will allow quantitative determination of body fat volume in the abdomen e.g. subcutaneous/visceral adipose tissue (SAT/VAT) depots, which have been shown to have an important role in insulin resistance [22, 23]. TZD therapy has shown to increase 'good' SAT and have a concomitant decrease in 'bad' VAT and liver fat in patients with diabetes but has not been studied in patients with pancreatic cancer related weight loss.

MRI examination will be performed on a clinical whole body system (Philips Achieva) at 3.0 Tesla at Rogers MRI Center equipped with a dedicated transmit/receive body coil and images will be interpreted by a dedicated study radiologist,(Department of Radiology). Scan protocol include a preliminary localizing sequence and a 3D multi-echo spoiled gradient echo sequence, with scan parameters optimized for fat quantification as previously described [21].

We propose this study to determine, what is the effect of PPAR γ agonist therapy with pioglitazone on adiponectin levels and markers of insulin sensitivity (fasting glucose, OGTT 0, 2 hour, I/G ratio) in pancreatic cancer patients. In addition we will evaluate the effects of pioglitazone therapy on weight, ECOG functional status, quality of life and disease response.

In order to differentiate pioglitazone related effects from chemotherapy related effects we will enroll a cohort of pancreatic cancer patients for correlative analysis only and will serve as a control arm. These patients will meet all eligibility criteria as detailed above but will not receive pioglitazone. **Pioglitazone**

General: Pioglitazone is one of two currently available PPAR γ agonists on the market. It is sold in the US under the name ActosTM. The other drug in this class on the market is rosiglitazone (AvandiaTM).

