Diabetes Mellitus Aggravated	8.1	5.1
Pharyngitis	0.8	5.1

Rationale for the Selection of Dose and Schedule

We plan to prescribe pioglitazone 45 mg per mouth daily, which is the maximum U. S. Food and Drug Administration (FDA) approved dose for the treatment of type 2 diabetes mellitus. Pioglitazone has been extensively prescribed in humans at the planned doses for this study. The safety and toxicity profile of pioglitazone is well established. We do not expect a higher than usual toxicity in patients with pancreas cancer receiving pioglitazone.

IV. Schema

This is an open label, double arm Phase 2 study. We plan to enroll 15 patients with adenocarcinoma of the pancreas to this study of oral pioglitazone 45 mg daily. Patients are allowed to continue on antineoplastic therapy while on this study and this will be determined by the treating physician.

A control cohort of up to 10 patients will be enrolled for correlative (blood and radiological) testing alone. These patients will meet all criteria set forth for the study and follow the same study visits, but not be treated with pioglitazone.

V. Hypothesis

Prior studies have shown that a significant proportion of patients with metastatic pancreas cancer have metabolic changes consistent with insulin resistance. Treatment of insulin resistance in patients with metabolic disorders like type 2 diabetes mellitus is associated with improved outcomes and less morbidity. We propose an exploratory clinical trial to study as a primary aim, the effects of the oral inhibitor of the peroxisome proliferator- activated receptor gamma (PPAR γ) pioglitazone in markers of insulin resistance in patients with pancreas cancer.

Our primary hypothesis is that patients with pancreas cancer will have significant improvements in markers of insulin resistance when treated with pioglitazone.

As secondary aims, we will evaluate changes in cancer related symptoms, performance status, and weight. We will also evaluate the objective response of measurable lesions and the time to disease progression in patients with pancreas cancer. MRI will be used to assess for changes in body fat distribution and changes in intratumor fat content (UT Southwestern and PHHS patients ONLY). We will compare change in blood biomarkers and MRI between the pioglitazone and control arms.

VI. Objectives

Primary objective

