We plan to enroll fifteen patients with metastatic or locally advanced pancreas cancer into a double arm pilot exploratory study of oral pioglitazone 45 mg daily.

Treatment will be administered for 8 weeks and then stopped.

Control Arm:

Up to ten patients meeting eligibility criteria will be enrolled in the control arm. Patients will be treated per standard of care treatment at the discretion of the treating team and will not be treated with pioglitazone.

Treatment arm assignment:

Treatment arm will be assigned by the principal investigator or treating MD at their discretion. Given the exploratory nature of this study, randomization will not be performed.

Control arm patients can include the following examples:

- patient declines pioglitazone therapy but agrees to biomarker testing (Adiponectin, a hormone made by fat cells, will be measured). Additional assays may be performed
- Patient is enrolled in another clinical trial which does not allow experimental therapy (pioglitazone) to be given. The protocol of the patient's study will be reviewed to ensure biomarker testing (Adiponectin, a hormone made by fat cells, will be measured) as defined in this study is not specifically prohibited.

- Patients enrolled after completion of the 15 study arm patients
- Other patients as deemed appropriate by the PI or co-Is

A. Recruitment

Eligible study patients will be screened, recruited, and enrolled at the following institutions:

1. University of Texas Southwestern Medical Center at Dallas:
 - a. Harold C. Simmons Comprehensive Cancer Center
 - b. University Hospital – Zale Lipshy
 - c. University Hospital – Saint Paul
2. Parkland Health and Hospital System (PHHS)
3. VA North Texas (Dallas)

Study patients will be recruited from the practices of the PI and co- investigators. Potentially eligible patients will be approached by their health care providers who can refer them to the study coordinator for screening. All patients being considered for the study and eligible must sign an informed consent for the study prior to any study specific procedures.

IX. Eligibility Criteria

Inclusion Criteria

Inclusion Criteria	Reason
Signed informed consent	Document patient participation and understanding of study requirements
Histologically proven adenocarcinoma of the pancreas	Disease of interest
Radiologically measurable disease	Target lesion to follow response to therapy

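### No masking to arm or scan order is specified for the MRI fat reads, so secondary endpoints e and f are needlessly open to reader expectation

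*Combined protocol and SAP*

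**What the plan says.** **Reader.** The MRI part of the background names the scanner, field strength, coil and sequence, and then says that "images will be interpreted by a dedicated study radiologist".

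**Measures.** Section XVI, item 7, says that "MRI will quantitate changes in a) intratumoral fat deposition in pancreatic cancer" and in visceral and subcutaneous fat. Tumour fat is measured as a proton density fat fraction (PDFF). For the abdominal depots, "MRI will allow quantitative determination of body fat volume in the abdomen", split into subcutaneous (SAT) and visceral (VAT) adipose tissue.

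**Expected direction.** The background says that "TZD therapy has shown to increase 'good' SAT and have a concomitant decrease in 'bad' VAT and liver fat". It places that finding in patients with diabetes and adds that it has not been studied in weight loss related to pancreatic cancer.

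**Design.** The Schema says: "This is an open label, double arm Phase 2 study". Section VIII says: "Treatment arm will be assigned by the principal investigator or treating MD at their discretion", and that "randomization will not be performed".

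**Role of the data.** Section VII lists MRI change as secondary endpoint e, a pilot in 8-10 patients picked by the investigators, and the between-arm comparison of serum and MRI changes as secondary endpoint f. Section XX.B labels both the MRI assessment and the comparison of arms exploratory.

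**The concern.** Endpoint e is a before/after change and endpoint f compares such changes between arms. A measurement habit that a reader applies equally to every scan cancels in the before/after difference. A habit that depends on knowing which scan followed pioglitazone does not cancel, and adding patients does not average it out.

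The plan leaves that route open. The trial is open label, a direction for SAT and VAT is written into the protocol, and nothing in the plan keeps arm or scan date from the reader. What is at stake is the credibility of a pilot MRI signal. The adiponectin, glucose and insulin results do not depend on it.

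**Working it through.** **1. Search for a masking provision.** The places that deal with MRI are:

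- the background;
- the Hypothesis section (V);
- objective 5 (VI) and endpoints e and f (VII);
- the baseline, week 8 and early-termination visits (XIII.B and XIII.F);
- Imaging Procedures (XIII.G);
- the Schedule of Events and its footnotes;
- XVI item 7;
- XX.B.

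Between them they give the equipment, the timing of the two scans, who may be scanned and what is measured. None mentions masking to arm, patient or date, the order of reading, a repeat read, or how the tumour region and the SAT/VAT boundaries are drawn. The finding is therefore silence, not a statement that reads are unmasked.

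**2. What knowledge of arm or order would do.** Write a patient's read change as

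D = true change + (error on the second scan − error on the first scan).

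If the reader's systematic error is the same on both scans, the bracket averages to zero. If knowing the order shifts it by δ, the mean change for endpoint e is off by δ at any n.

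For endpoint f the error is δ(pioglitazone) − δ(control). Knowing only the order, and acting on it equally in both arms, cancels in f but not in e. Knowing the arm as well affects f. Both date and arm labels therefore matter.

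**3. Is there a size?** The only sample-size figure in the documents is for adiponectin: n = 15, change 0.4, SD 0.5, alpha 0.05, stated power 82%. A two-sided one-sample t-test has noncentrality (0.4/0.5) × √15 = 3.10 and power 82.1%, so that figure reproduces. It says nothing about MRI. The documents give no MRI effect, variance or reader error, so δ cannot be estimated.

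**4. Illustration on assumed values only.** Suppose there is no true change, and a paired two-sided t-test at 0.05 is used (the plan names no MRI test). Let expectation shift the mean by b SDs of the change. The test statistic is noncentral t with n − 1 degrees of freedom and noncentrality b√n; for b = 0.5 that is 1.41 at n = 8 and 1.58 at n = 10. The chance of a significant result is:

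| Assumed shift b | n = 8 | n = 10 |
|---|---|---|
| 0 | 5% | 5% |
| 0.25 | 9% | 11% |
| 0.5 | 23% | 29% |
| 0.75 | 45% | 56% |

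For a fixed shift, the larger n gives more false signals. The table shows how such a bias behaves; it does not predict its size here.

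**5. Number of reads.** With two scans per patient, 8-10 patients give 16-20 scans. The text is not clear on controls. Endpoint e ties the 8-10 to patients treated with pioglitazone. The baseline visit and the Schedule footnotes give 8-10 without naming an arm. The Schema gives up to 10 controls radiological testing, and XIII.F applies the same procedures to both arms. If controls are additional, the upper bound is (10 + 10) × 2 = 40 scans.

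**The case against.** The strongest case on the other side is that nothing has been shown to go wrong.

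- **The documents do not say that reads are unmasked.** A reader might infer from the open-label design that the radiologist knows arm and date. The documents do not support that: they place the scans at a research MRI centre and never say what the reader is told. This stands, and the point is confined to masking not being specified.
- **The stated direction does not cover the tumour.** A reader might infer that higher or lower tumour fat is also predicted. No MRI section states a direction for intratumoral fat. This stands. The expectation argument is explicit for SAT and VAT only, and there it is borrowed from diabetes.
- **The measures are quantitative.** PDFF and fat volumes are not subjective grades, and the technique is taken from a cited source that cannot be checked here. This narrows the room for judgement. It does not close it, because the plan describes neither region placement nor depot outlining as automated or rule-based.
- **The data carry little weight.** Endpoint e is a pilot, XX.B calls both analyses exploratory, and no decision rests on them. This stands and limits the importance of the point. Even so, e and f are listed secondary endpoints, and a pilot is useful only if its signal can be believed.

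**Conclusion.** The point holds as a low-cost improvement, not as a demonstrated flaw. One dedicated radiologist interprets the scans in an open-label, non-randomised trial, and the plan specifies no masking to arm, date or before/after order. Bias in endpoints e and f is possible on two conditions: that outlining involves reader judgement, and that the reader knows arm or order. The documents settle neither. Its size cannot be stated, and the primary laboratory markers are untouched.

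Two stronger readings should be resisted. Having a single reader is not the defect; one consistent reader is kept in the remedy. Nor would masking make the arm comparison sound. Discretionary arm assignment and discretionary choice of MRI patients bring selection bias that no reading procedure removes.

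**What to change.** In XIII.G and XVI item 7, state that:

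- the same radiologist makes the quantitative PDFF and SAT/VAT reads in batches;
- patient, arm and date labels are removed, and each patient's scans are presented in random order;
- region outlines and values are saved and locked before unmasking.

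Also say whether control-arm scans are counted within the 8-10 patients or come on top.

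**Cost.** Study staff de-identify and shuffle about 16-20 scans, or up to about 40 if control-arm scans are additional. No extra scan, visit or reader is needed. Research values arrive in batches instead of scan by scan; no treatment decision in the plan uses them. Masking may be imperfect where visible tumour change gives away the order, but the explicit labels are gone. If masked reading is already the practice, the cost is the added text.
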